In the ROOBY study (CSP # 517) (Shroyer 2009), one year MACE rates were 9.9% in the OVH group and 15.3% in the EVH group ($p=0.0025$). The executive committee for the REGROUP study assumes that during the REGROUP study, 15.5% of the subjects in the EVH group will experience MACE in the first year post surgery. The committee also expects a 6 percentage point improvement in the one-year MACE rate in the OVH group.

B. Sample size calculation for the REGROUP study

To detect the expected 6 percentage point difference in one-year MACE rates between EVH (15.5%) and OVH (9.5%), a sample size of **545 in each group** will be required at 85% power, 5% type-I error rate and with a two-sided test. A sensitivity analysis was also done with various scenarios which are shown in the Table 3. Since, it would be possible to capture the majority of the MACE from the VA databases even if the subjects drop out before the one-year clinic visit, a relatively small inflation factor of 5% is used to inflate the sample size to account for the drop-outs. Approximately, 1150 subjects need to be randomized in the study to achieve the said power.

	Case 1	Case 2	Case 3	Case 4	Case 5	Case 6	Case 7	Case 8	Case 9
Tails	2	2	2	2	2	2	2	2	2
Proportion 1 (%)	9.9	9.9	9.9	9.5	9.5	9.5	10	10	10
Proportion 2 (%)	15.3	15.3	15.3	15.5	15.5	15.5	16	16	16
Alpha	0.05	0.05	0.05	0.05	0.05	0.05	0.05	0.05	0.05
Power (%)	90	85	80	90	85	80	90	85	80
Allocation ratio	1:1	1:1	1:1	1:1	1:1	1:1	1:1	1:1	1:1
Sample Size	792	677	592	637	545	476	659	563	492
Total Sample Size	1584	1354	1184	1274	1090	952	1318	1126	984
Attrition = 5%	1667	1425	1246	1341	1147	1002	1387	1185	1036
Attrition = 10%	1760	1504	1316	1416	1211	1058	1464	1251	1093
Attrition = 15%	1864	1593	1393	1499	1282	1120	1551	1325	1158

Table 3: Various sample size scenarios for the REGROUP study

Based on the one-year MACE rate difference between EVH and OVH groups as obtained from CSP 517, if we assume at the end of the active follow-up period (approximately 4.5 years from the beginning of the recruitment process) difference in survival rates (i.e., the proportion of subjects who will not experience

MACE) between the two harvesting groups will be approximately 8 percentage point (i.e., 83.5% in the EVH and 91.5% in OVH), a sample size of 532 per group will be required to achieve a power of 97.5%. So, the sample size of 1150 (with approximately 7% attrition rate accounted for) will provide adequate power to the time-to-MACE event primary outcome.

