C. Duration of Study/Number of Participating Sites

Based on the experience of previous CSP studies on CABG performed in the last decade (2000-2010) (e.g. CSP #517 ROOBY and CSP #474 RADIAL), a two subject/month/site enrollment rate was assumed to be a reasonable enrollment rate for this study. With this assumption, various scenarios were created to find an optimum balance between the number of sites, the study duration (which includes enrollment period and follow-up period) and the estimated budget. The chosen scenario was with 16 sites around the country where both EVH and OVH are currently practiced. With 16 sites and two subjects/month/site rate of enrollment, the enrollment period was found to be approximately, three years which would be followed by a minimum of one-year follow-up for the last subject randomized into the study. This will allow approximately 4 – 4.5 years of active follow-up of all randomized subjects followed by additional 2 years of passive follow-up using the VA databases. The total duration for the 16 participating sites will be approximately 6.5 years.

D. Statistical Analysis Plan

1. Intent-to-treat (ITT) analysis

Intent-to-treat population is defined as the population of subjects who will be randomized to either of the harvesting technique groups – EVH or OVH. The subjects will be categorized (in terms of their harvesting technique group assignment) based on their initial randomized group irrespective of conversion before surgery and will be included in analyses irrespective of their status – completer or drop out of the study before completion. Analyses of all outcome measures – primary and secondary – will use ITT population.

All statistical tests will be 2-sided and the primary MACE outcome will be tested at 5% level of significance. SAS will be used to conduct all the statistical analyses.

2. Primary Outcome Measure

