A typical Kaplan-Meier curve showing survival probabilities in two treatment groups is shown in Figure 3.

A test of equality across strata will also be performed to decide which predictor variables to include in the final model. For categorical variables log-rank tests, a non-parametric test, will be used and for continuous variables univariate Cox proportional hazard regression, a semi-parametric model, will be used. The results from the log-rank tests and univariate Cox proportional hazard regressions will be presented in the formats as shown in Tables 7 and 8.

Table 7: Test of Equality over Strata

Variable	Test (Log-Rank/MLE)	Chi-Square	Df	Pr > Chi-Square

Cox's Proportional Hazards models will be used to investigate the effect of harvesting technique on the time until MACE adjusted for other potential influential variables, such as, age, gender, harvester's experience etc. The predictors that are identified in the previous step will be included in the model. The results from the modeling will be presented in the format as shown in Table 8.

Table 8: Cox Proportional Hazards Model to evaluate effect of EVH/OVH on time-to-MACE adjusted for predictor variables

Variable	Df	Parameter Estimate	Standard Error	Chi-Square	Pr > Chi-Square

Secondary Outcome Measures:

1. One-year MACE:

Patients who will suffer any one of these three outcomes within the first year after index CABG will be counted towards calculating the proportions of patients with MACE (yes/no) in each harvesting technique group – patients with endoscopic vein grafting or patients with open vein grafting. Only the first event will be considered as a MACE event. These two proportions will be compared using a chi-square test. MACE data at one-year post surgery will be presented as shown in Table 9. Tables 10, 11 and 12 provide the format for the components of MACE – for example, death (all cause), MI, and repeat revascularization.

Table 9: MACE distributions in harvesting technique groups at one-year post surgery

Harvesting MACE	OVH	EVH	Total
No			
Yes			
Total			
ChiSq =	p-value =		

Table 10: Death (all cause) distributions in harvesting technique groups

Harvesting Death (all Cause)	OVH	EVH	Total
No			
Yes			
Total			
ChiSq =	p-value =		

Table 11: MI distributions in harvesting technique groups

Harvesting MI	OVH	EVH	Total
No			
Yes			
Total			
ChiSq =	p-value =		

Table 12: Revascularization distributions in harvesting technique groups

Harvesting Revascularization	OVH	EVH	Total
No			

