VA COOPERATIVE STUDY #588

RANDOMIZED ENDO-VEIN GRAFT PROSPECTIVE – REGROUP TRIAL

Site Selection Process: Vein Harvester Qualification Policy

1. VA sites with active Cardiac Surgery Programs are contacted with introductory letter including executive summary and relevant manuscripts via email.
2. Interested sites provide high-level overview of the sites Cardiac Surgery Service eligibility criteria:
 - established EVH program >2years,
 - sufficient isolated CABG volume to enroll 2-3 subjects/month x3 years,
 - willingness to randomize to EVH vs. OVH,
 - at least one harvester experience includes > 100 EVH with conversion rate \leq 5%,
 - ability to competently provide care for OVH procedure.
3. All potential sites complete CSP #588 Form 15 for each individual harvester who is expected to perform the vein harvesting procedure as part of normal daily job duties during the course of study participation at the site. The forms are signed by the site Principle Investigator (site surgeon investigator) as verification.
4. Each completed form is submitted to and reviewed by the Study Chair's office.
5. A Subcommittee of the Executive Committee will review each site case by case to determine eligibility status and designate each site as one of the following:
 - A. Site with at least one harvester experienced in BOTH EVH and OVH confirmed by the site surgeon investigator => site confirmed as qualified for study participation and harvester assigned a code by CSPCC.
 - B. Site with at least one harvester experienced in EVH but NOT OVH confirmed by the site surgeon investigator => site confirmed as qualified for study participation only IF a designated harvester for OVH is identified, assigned a code by CSPCC, and MUST be immediately available, in addition to the EVH harvester, at time of randomization and harvesting (i.e. the site surgeon investigator).
 - I. Site with NO harvester experienced in EVH and/or incapable of providing OVH procedure=> site is INELIGIBLE for study participation at this time regardless of interest level or CABG volume.

Subcommittee Members: [name] [name], FETCS; [name], PA-C; [name], CRNP

CSP #588

RANDOMIZED ENDO-VEIN GRAFT PROSPECTIVE – REGROUP TRIAL

Version 1.2 Protocol

October 1, 2013

F-1

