3.6 Sample Size

In the ROOBY study (CSP # 517) (Shroyer et al. 2009), 1-year MACE rates were 9.9% in the OVH group and 15.3% in the EVH group ($p=0.0025$). The executive committee for the REGROUP study assumed that during the REGROUP study, 15.5% of the participants in the EVH group will experience MACE in the first year post surgery. The committee also expects a 6 percentage point improvement in the 1-year MACE rate in the OVH group.

To detect the expected 6 percentage point difference in 1-year MACE rates between EVH (15.5%) and OVH (9.5%), a sample size of 545 in each group will be required at 85% power, 5% type-I error rate and with a two-sided test. Since, it would be possible to capture the majority of the MACE from the VA databases even if participants drop out before the one-year clinic visit, a relatively small inflation factor of 5% is used to inflate the sample size to account for the drop-outs. Thus, a total of 1,150 participants need to be randomized in the study to achieve the said power.

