The patient characteristics would be presented by medical center and by harvesting technique group for the DMC. Significant imbalances of these patient characteristics between the harvesting technique groups may indicate a need to use these characteristics as covariates during the analysis of the outcome measures. Formal testing of the differences between groups will be done at the study's conclusion using appropriate statistical tests - analysis of variance technique will be used to test characteristics that are continuous in nature, while chi-square technique will be used for the test characteristics that are discrete in nature.

As with any clinical trial, the safety of the patient will be of utmost concern. Safety will be monitored closely during the course of the study. The DMC Report will include data on incidence of adverse events by treatment group. It will also include data on early terminations and treatment dropouts. The adverse event data will also be reported in the primary study manuscript. Data will be collected on adverse events throughout the study starting immediately after the patient signs the informed consent form.

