equality (null hypothesis) of the survival function estimates across strata (OVH and EVH) will employ either the log-rank or Wilcoxon test. Multivariable survival analyses applying a Cox proportional hazards regression model will be performed to investigate the effect of SVG harvesting technique on time-to-MACE, adjusting for other potentially influential baseline characteristics, such as age, gender, harvester's experience, etc. (TABLE 25). Assumptions of the model (i.e., non-informative censoring, proportional hazards) will be checked. If assumptions appear to be violated, alternative methods will be explored (e.g., piecewise, time-varying covariates). A type I error rate of $\alpha = 0.05$ will be used throughout. Confidence intervals will be two-sided with a 95% confidence level.

The hypothesis for the primary aim of this study is:

H1: A significantly smaller proportion of CABG subjects with SVGs harvested by open technique will experience MACE post-surgery compared to CABG subjects with SVGs harvested by endoscopic technique during the active follow-up period.

The hypothesis for the primary aim of this study will be supported when an increased risk of MACE is observed among participants randomized to EVH, confirmed with a hazards ratio (HR) > 1.00 for EVH vs. OVH and a significant corresponding p -value $< \alpha$.

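### The plan leaves open which test decides H1 and which covariates enter the Cox model: the protocol selects covariates from trial data, and the SAP neither adopts nor withdraws that step

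*Protocol*

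**What the plan says.** **Protocol.** Section XVII.D.1 sets the level: "All statistical tests will be 2-sided and the primary MACE outcome will be tested at 5% level of significance". Section XVII.D.2 uses the log-rank test for the null of equal survival functions and a Cox model to examine the effect of harvesting technique adjusted for other variables. Appendix D, under Primary Outcome Measure, adds a selection step: "A test of equality across strata will also be performed to decide which predictor variables to include in the final model". Categorical predictors are tested by log-rank and continuous ones by univariate Cox regression. Whatever is identified goes into the model. No p-value threshold and no closed list of candidates is given.

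**Baseline imbalance.** Appendix D (DMC monitoring) and SAP 5.5.1 carry the same sentence: "Significant imbalances of these patient characteristics between the harvesting technique groups may indicate a need to use these characteristics as covariates". Formal tests of imbalance are to be run at the end of the study.

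**SAP.** Section 7.1 leaves the unadjusted test as a choice between log-rank and Wilcoxon. It names age, gender and harvester experience as examples of covariates and leaves the list open. H1 is supported when an increased risk with EVH is "confirmed with a hazards ratio (HR) > 1.00 for EVH vs. OVH" and the corresponding p-value is significant. The only table shell with a hazard ratio is Table 25, the multivariable Cox model, whose covariate rows are placeholders. Protocol XVII.H requires departures from the protocol's statistical plan to be stated in the SAP. None is stated on this point.

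**The concern.** A reader holding both documents cannot say which p-value will decide H1, or which variables will stand beside treatment in the Cox model. The protocol's selection rule uses the same outcome data that test the hypothesis. The imbalance route is optional, so using it is a further decision taken after the data are in.

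The people involved make this more than a formality. Under Appendix D (Study Management) the study biostatistician attends the unblinded parts of DMC meetings and also conducts the final analyses. Covariates left open could thus be settled by someone who has seen outcomes by arm. At stake is the credibility of the primary result, above all if the estimate falls near the significance boundary. SAP 7.2 analyses H3 in the same way with the same tables, so the gap carries over.

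**Working it through.** **1. The plan's own figures.** SAP 3.6 states "a sample size of 545 in each group will be required at 85% power, 5% type-I error rate and with a two-sided test". Pooled two-proportion formula, 15.5% vs 9.5%, mean 12.5%:

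- [1.96 × √(2 × 0.125 × 0.875) + 1.036 × √(0.155 × 0.845 + 0.095 × 0.905)]² / 0.06² = (0.917 + 0.483)² / 0.0036 ≈ 544, i.e. 545 after rounding up. 1,090 / 0.95 = 1,147, stated as about 1,150.
- Time-to-MACE (Protocol XVII.B, MACE-free "83.5% in the EVH and 91.5% in OVH"): HR = ln 0.835 / ln 0.915 = 2.03. Freedman events at 97.5% power = (3.03 / 1.03)² × (1.96 + 1.96)² ≈ 133. Mean event proportion (0.165 + 0.085) / 2 = 0.125. 133 / 0.125 = 1,064, i.e. 532 per group.

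Both reproduce. Neither depends on covariate adjustment, so nothing here changes the sample size.

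**2. What could decide H1.**

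| Candidate | For | Against |
|---|---|---|
| Log-rank | Named for the null in Protocol XVII.D.2 | Yields no hazard ratio; SAP offers Wilcoxon as an alternative |
| Wilcoxon | Allowed by SAP 7.1 | Not in the protocol; yields no hazard ratio |
| Adjusted Cox | Only hazard-ratio shell (Table 25) | SAP does not call the H1 hazard ratio adjusted |
| Unadjusted Cox | Fits the H1 wording | Not described for treatment in either document |

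The documents do not settle this.

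**3. Size.** No closed formula applies. Two simulations were used; every setting except N = 1,150 and the 5% level is an assumption.

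- A: 12 candidates, 6 prognostic at HR 1.42 per SD, about 160-220 events.
- B: 10 candidates, 5 prognostic at log-HR 0.25 per SD (HR 1.28), selection at p < 0.05, follow-up uniform over 1-4 years, about 180-200 events.

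Rejection rates, two-sided 5%:

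| Analysis | A, null (1,500 runs) | A, HR 1.45 (800) | B, null (10,000) | B, HR 1.35 (3,000) |
|---|---|---|---|---|
| Unadjusted (A log-rank, B Cox) | 5.2% | 63.4% | 4.8% | 55.0% |
| Prespecified covariates | 6.2% | 71.6% | 5.1% | 58.5% |
| Outcome-screened | 6.0% | 71.6% | 5.1% | 58.4% |
| Imbalance-screened | 4.7% | 64.5% | 4.8% | 55.5% |
| Both rules together | not run | not run | 5.1% | 58.3% |
| Most favourable result | 7.8% | not run | 6.2% | 61.8% |

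The most favourable result is taken over the log-rank and the two screened models in A, and over the unadjusted and three data-selected models in B. The Monte Carlo standard error at the null is about √(0.06 × 0.94 / 1,500) = 0.6 points in A and √(0.05 × 0.95 / 10,000) = 0.2 points in B. In B, the unadjusted model and the model using both rules disagree on significance in 2.2% of null trials and 9.3% at HR 1.35.

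Two limits apply. These rates count both directions; H1 also needs HR > 1, so by symmetry the error in the claimed direction is about half (3.1% and 3.9% against 2.5%). Neither simulation includes the Wilcoxon option.

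**The case against.** The strongest reply is that the SAP governs the final analysis and has in effect dropped the screening. SAP 7.1 confines the test of equality across strata to the two arms, and no SAP shell matches protocol Table 7, where the screening results would go. That is a fair reading. But the SAP does not declare the change, as XVII.H requires, and it puts no fixed list in its place. The gap stays, though it is better called undeclared and open than an operative screening rule.

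Four stronger readings are tempting and not supported:

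- *The adjusted Cox model decides H1.* A reader may infer this from Table 25. The documents do not say it, and the protocol attaches the null hypothesis to the log-rank test.
- *The plan's error rate is 7.8%.* That needs a rule of claiming success if any of three tests is significant. Neither document permits such a rule.
- *Screening loses precision.* It does not: 71.6% against 71.6% in A, 58.4% against 58.5% in B. Only imbalance selection used alone falls short, and the documents never make it the sole rule. At the design HR of 2.03, with planned power of 97.5%, adjustment could change power little in any case.
- *Harvester experience is a post-randomisation covariate.* Appendix F admits sites whose EVH harvester is not experienced in OVH if a separate OVH harvester is designated, who "MUST be immediately available, in addition to the EVH harvester, at time of randomization and harvesting". There, the operator's experience would follow the arm. But no text proposes using it. Form 05 records only the operator's professional category, Form 17 holds experience by harvester ID, Form 01 Q18c holds the assigned harvester, and SAP 7.1 calls the variable a baseline characteristic. What is missing is a definition.

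**Conclusion.** The concern holds as a gap in prespecification. The protocol states a data-driven covariate rule, and the SAP neither keeps nor revokes it. The covariate list is open, and the H1 criterion cites a hazard ratio and p-value whose source is not named. Any single rule applied mechanically is harmless in these simulations. With the choice left open, two-sided false positives could reach about 6-8% if the most favourable version were reported, and the significance verdict could turn on the model in about 2% of null trials and 9% at HR 1.35. These sizes depend on assumed numbers and strengths of covariates and on an assumed selection threshold. They show the order of magnitude and are not operating characteristics of the plan. The case rests on removing discretion at almost no cost.

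**What to change.** Before unblinding, amend the SAP as follows:

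1. Name one confirmatory test for H1: the log-rank, as in Protocol XVII.D, with the Wilcoxon option deleted. Ideally stratify by the randomisation factor (harvester within site), pooling small strata by a stated rule. The Table 11 shell lists 32 harvesters, so 1,150 / 32 is about 36 subjects per stratum.
2. Make the supporting estimate a Cox model stratified in the same way, with a fixed Form 02 list: age, diabetes, ejection fraction, SYNTAX score and one named risk score (VASQIP or STS). State the functional forms and the handling of missing covariate values. Say that the hazard ratio in the H1 criterion comes from this model and that the log-rank p-value decides.
3. Declare, under Protocol XVII.H, that the Appendix D screening and the imbalance-driven selection are dropped or kept only as sensitivity analyses.
4. If harvester experience is used, define it from the harvester assigned before randomisation (Form 01 Q18c linked to Form 17), and say whose ID counts at sites with separate EVH and OVH harvesters. With harvester-level strata its main effect cannot be estimated, so it can enter only under coarser strata such as site.

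Apply the same text to H3. The list should preferably be settled by someone who has not seen outcomes by arm. The cost is SAP wording and one declared departure from the protocol. No new data and no change in sample size are needed.

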Table 18 provides the format in which the logistic regression analysis results for the leg wound healings complications will be presented. Each of the covariates in the model will be presented with individual odds ratio and 95% Confidence Interval.

Table 18: Logistic Regression Analysis of Leg Wound Healing Complications Data at 6-week Post Surgery

	Odds Ratio	95% Confidence Interval	
		LL	UL
Harvesting Technique			
BMI			
Harvester Experience			
Age of patient			
Diabetes Status			
Smoking Status			

4. **Severity of Incisional Leg Pain:** Severe leg pain, due to incisions made during vein grafting, data will be collected at discharge and at six-week post CABG. Proportion of patients with severe pain (pain score 3 and above = yes) at each time point will be compared using chi-square statistics.

The results from the chi-square analysis will be presented with counts of 'yes' and 'no' in regards to severity of incisional leg pain in the two harvesting techniques as shown in Table 19.

Table 19: Severity of Incisional Leg Pain distributions in harvesting technique groups

Harvesting Severity of Leg Pain	OVH	EVH	Total
No			
Yes			
Total			
ChiSq =	p-value =		

5. **Quality of Life:** QoL scores, from VR-12 and Seattle Angina Questionnaire, will be computed at baseline, six-weeks, and 12 months post-surgery for the patients in both harvesting technique groups (EVH and OVH). Patients in the two groups will be categorized as “improved”, “no change” and “worse” based on their baseline scores. The proportions of patients in these three categories will be compared between the two groups using chi-square statistics. The actual scores from these measures will also be used to compare patients in the two harvesting technique groups using analyses of covariance techniques, where the baseline (pre-surgery) scores will be used as a covariate. The results from the chi-square analysis will be presented with counts of ‘yes’ and ‘no’ in regards to QoL scores categorized as “improved”, “no change” and “worse” in the two harvesting techniques as shown in Table 20. Table 21 provides the format in which the results from ANCOVA analysis will be presented.

Table 20: QoL/SAQ score distributions in harvesting technique groups

Harvesting QoL score	OVH	EVH	Total
Improved			
No Change			
Worse			
ChiSq =	p-value =		

Table 21: QoL/SAQ Scores by Harvesting Technique

Treatment Group	QoL Score		
	N	Mean	Standard Error
Covariate	Estimate	Std. Error	t-statistics
Harvesting Technique			
Baseline QoL Score			
Source	Df	F Statistics	p-value
Harvesting Technique			
Baseline QoL score			

SITE NO.	SUBJECT ID	ALPHA CODE	DATE FORM COMPLETED															

 	 	 	

				

 	 	 	 	

					

 	 	 	 	

					

 	 	 	 	

				
			Month Day Year															

FORM 01 - SCREENING RECORD

***Complete this form for all subjects undergoing a CABG procedure at your site and submit to the Perry Point Cooperative Studies Program within 48 hours of CABG procedure.**

INCLUSION CRITERIA

	No	Yes
1. Age 18 years or older?		
2. Elective or Urgent CABG-only (refer to protocol definition)?.....		
3. Median sternotomy approach?		
4. At least one coronary bypass planned using saphenous vein graft for conduit?		
5. Experienced EVH/OVH harvester and participating surgeon available for procedure?		

Answers to questions 1-5 must all be 'YES' for the subject to be eligible for enrollment

EXCLUSION CRITERIA

	No	Yes
6. Combined valve procedure planned?		
7. Moderate or severe valve disease (see definition of moderate/severe valve disease)?		
8. Hemodynamically unstable or in cardiogenic shock?		
9. Enrolled in another therapeutic or interventional study?		
(without special approval obtained for enrollment)		
10. Off-pump CABG procedure planned?		
11. Limited life expectancy less than 1 year?		
12. History of lower extremities venous stripping or ligation?		
13. Inability to provide informed consent?		

Answers to questions 6-13 must all be 'NO' for the subject to be eligible for enrollment

SITE NO.			
----------	--	--	--

SUBJECT ID			
------------	--	--	--

ALPHA CODE			
------------	--	--	--

ENROLLMENT

No Yes

14. Is the subject eligible to be enrolled into the REGROUP study? *If the answer to question 14 is NO, then STOP, SIGN form - this form is now complete.*15. If the subject is **eligible but not enrolled**, mark (x) in the one box that best describes the reason:

- Subject refused to sign Informed Consent*
- Eligibility status changed (e.g., died, treatment plan changed, etc.)*
- Site surgeon concerned about resources needed for on-site follow-up (cost, time, etc)*
- No reliable method of follow-up contact with the subject (e.g., no phone, etc.)*
- Primary reason subject preferred non-enrollment*
 - Subject prefers open vein harvest*
 - Subject prefers endoscopic vein harvest*
 - Reason other than vein harvest preference*

specify: _____

- Primary reason surgeon preferred non-enrollment*
 - Surgeon prefers open vein harvest for subject*
 - Surgeon prefers endoscopic vein harvest for subject*
 - Reason other than vein harvest preference.*

specify: _____*If the subject was not enrolled in the study, STOP, SIGN form - this form is now complete.***RANDOMIZATION** - If the subject is eligible and willing to be randomized, call CSPCC at [contact]

No Yes

16. Was the subject randomized into the study? *If Q 16 is Yes then go to Q 18. If Q 16 is No then go to Q 17 and the form is complete when signed.*

--	--	--

--	--	--	--

--	--	--	--

17. If the subject has signed the consent but was not randomized, mark (x) in the one box that best describes the reason:

Eligibility status changed

explain: _____

Subject changed mind after consent signed

explain: _____

Surgeon changed mind after subject signed consent

explain: _____

Other reason (specify): _____

18. If the subject is **randomized**, complete the following information:

a. Date subject was randomized

--	--

--	--

--	--	--	--

Month Day Year

b. Time subject was randomized (Military Time)

--	--

--	--

hour : min

c. Assigned harvester ID Number

--	--

d. Assigned surgeon ID Number

--	--

e. Envelope Number

--	--

 -

--	--	--	--

f. To what treatment was subject randomized?

--

 EVH

--

 OVH

--

S.I. or Participating Surgeon Signature _____

Print Name: _____

Print name of the person completing this form if other than the site coordinator: _____

SITE NO.

--	--	--

SUBJECT ID

--	--	--	--

ALPHA CODE

--	--	--	--

DATE OF ASSESSMENT

--	--	--

Month

--	--

Day

--	--	--	--

Year

FORM 02 – BASELINE INFORMATION

COLLECT DATA FROM THE EXISTING MEDICAL RECORD FOR RANDOMIZED SUBJECTS.

IDENTIFICATION DATA

1. DATE OF BIRTH:

--	--

--	--

--	--	--	--

month *day* *year*

DEMOGRAPHIC DATA

2. GENDER:

Male Female

3. RACE: American Indian or Alaskan Native

Asian or Pacific Islander

Black, not of Hispanic origin

Hispanic

White, not of Hispanic origin

Other, specify: _____

4. MARITAL STATUS:

Married/remarried

Divorced

Separated

Widowed

Never married

5. EDUCATION:

Completed Graduate/professional training

Standard college/university graduate

Partial college training

High school graduate/GED

< High school

SITE NO.	SUBJECT ID.	ALPHA CODE									

 
			
 
				
 
			
 
				
 
			
 
			

MILITARY SERVICE HISTORY:6. Served in the military? No Yes

a. If Yes, when did the patient serve: (mark 'x' all that apply)

 World War I	 Balkans conflict
 World War II	 Afghanistan conflict
 Korean conflict	 Iraq conflict
 Vietnam conflict	 Other war/conflict, specify: _____
 Gulf War	 Peace time

b. If Yes, served outside the U.S.: No Yes

c. If Yes, specify branch:

 Army	 Coast Guard
 Air Force	 National Guard (active duty)
 Navy	 Merchant Marine
 Marines	

PRE-OPERATIVE CLINICAL DATA, CO-MORBIDITIES7. Diabetes: No Yesa. If Yes, how controlled? None Diet Oral Hypoglycemic Insulin8. Hypertension: No Yes9. Hyperlipidemia: No Yes10. Depression : No Yes11. Chronic Renal Disease: No Yesa. If Yes, requires dialysis? No Yes12. Chronic Liver Disease: No Yes13. Peripheral Vascular Disease: No Yes14. Cerebral Vascular Disease: No Yesa. If Yes, CVA? No Yesb. If Yes, specify interval: <2weeks >2weeks

SITE NO.	SUBJECT ID.	ALPHA CODE											

 	 	 	

				

 	 	 	 	

					

 	 	 	 	

				

15. Chronic Lung Disease: No Yesa. If Yes, FEV₁:

--	--	--

 % predicted16. Immunosuppressive Therapy: No Yes17. Tobacco use > 100 cigarettes/lifetime: No Yes

a. If Yes, last use prior to surgery:

 < 7 days ≥ 3 months but < 1 year ≥ 7 days but < 3 months ≥ 1 year18. Alcohol use > 1 ounce/day: No Yes

a. If Yes, last use prior to surgery:

 < 7 days ≥ 3 months but < 1 year ≥ 7 days but < 3 months ≥ 1 year19. Other major comorbidity: No Yes

a. If Yes, specify: _____

20. Residential Status (resides with):

 Spouse Assisted Facility Family/other Alone

21. Functional Status: (ability to complete activities of daily living)

 Independent Needs Assistance Dependent**CARDIAC STATUS**22. Previous CABG Procedure: No Yes If Yes, Date:

--	--

--	--

--	--	--	--

month *day* *year*23. Previous Valve Procedure: No Yes If Yes, Date:

--	--

--	--

--	--	--	--

month *day* *year*

SITE NO.	SUBJECT ID.

ALPHA CODE

24. Previous PCI Procedure: No Yes If Yes, Date:

--	--

--	--

--	--	--	--

 month day year

a. If Yes, specify interval: \leq 6 hours $>$ 6 hours

25. Myocardial Infarction: No Yes If Yes, Date:

--	--

--	--

--	--	--	--

 month day year

a. If Yes, specify interval: \leq 6 hours $>$ 7 days but \leq 21 days

$>$ 6 hours but \leq 24 hours $>$ 21 days

$>$ 1 day but \leq 7 days

26. Peak Cardiac Biomarkers (if available); No Yes If Yes, Date:

--	--

--	--

--	--	--	--

 month day year

If yes, you must complete A, B, OR C below

A. Peak Cardiac Troponin I

1. Peak Cardiac Troponin I (ng/mL):

--	--

 .

--	--

2. Reference Range (ng/mL):

--	--

 .

--	--

 to

--	--

 .

--	--

B. Peak Cardiac Troponin T

1. Peak Cardiac Troponin T (ng/mL):

--	--

 .

--	--

2. Reference Range (ng/mL):

--	--

 .

--	--

 to

--	--

 .

--	--

C. Peak CPK/MB Panel

1. Peak Total CPK (U/L):

--	--	--	--

2. Total CPK Reference Range (U/L):

--	--

 to

--	--	--

3. Peak CK-MB (ng/mL):

--	--

 .

--

4. CK-MB Reference Range (ng/mL):

--

 to

--	--

 .

--

5. Peak CK-MB Index (%):

--	--

 .

--

6. CK-MB Index Reference Range (%):

--	--

 .

--

 to

--	--

 .

--

SITE NO.

--	--	--

SUBJECT ID.

--	--	--	--

ALPHA CODE

--	--	--	--

27. Heart Rate by ECG: <100 ≥100 Date:

--	--

 month

--	--

 day

--	--	--	--

 year28. Arrhythmia by ECG: No Yes If Yes, Date:

--	--

 month

--	--

 day

--	--	--	--

 year
a. If Yes, specify:
 Atrial fibrillation Pacemaker
 Atrial Flutter Other, specify: _____29. Cardiomegaly by CXR: No Yes If Yes, Date:

--	--

 month

--	--

 day

--	--	--	--

 year30. Ejection fraction by ECHO:

--	--	--

 % Date:

--	--

 month

--	--

 day

--	--	--	--

 year31. LV aneurysm by ECHO: No Yes If Yes, Date:

--	--

 month

--	--

 day

--	--	--	--

 year

32. Presentation on Admission: (mark only one)

No symptoms or angina Unstable angina
 Symptoms, non-ischemic Non-ST elevation MI
 Stable angina ST elevation MI

a. If experiencing angina classify by CCSS: Class I Class II Class III Class IV33. Congestive Heart Failure: No Yesa. If Yes, classify by NYHA: Class I Class II Class III Class IV34. Presence of Pulmonary Rales: No Yes If Yes, Date:

--	--

 month

--	--

 day

--	--	--	--

 year35. Infectious Endocarditis: No Yes If Yes, Date:

--	--

 month

--	--

 day

--	--	--	--

 year
a. If Yes, specify type: Treated Active36. Cardiogenic Shock: No Yes If Yes, Date:

--	--

 month

--	--

 day

--	--	--	--

 year

--	--	--

--	--	--	--

--	--	--	--

37. Resuscitation: No Yes If Yes, Date:

--	--

 month

--	--

 day

--	--	--	--

 year
38. Inotropes: No Yes

39. Status of Index CABG Procedure:
 Elective Emergent *
 Urgent Emergent salvage *

(*NOTE: 'Emergent' and 'Emergent salvage' are exclusion criteria.)

VALVE DISEASE BY ECHO TYPE (Note: 'Moderate' and 'Severe' are exclusion criteria.)

40. Aortic regurgitation (Insufficiency)
 None Trivial Mild (1+) Moderate (2-3+) Severe (4+)

41. Aortic stenosis
 None Trivial Mild (1+) Moderate (2-3+) Severe (4+)

42. Mitral regurgitation (Insufficiency)
 None Trivial Mild (1+) Moderate (2-3+) Severe (4+)

43. Mitral stenosis
 None Trivial Mild (1+) Moderate (2-3+) Severe (4+)

44. Tricuspid regurgitation (Insufficiency)
 None Trivial Mild (1+) Moderate (2-3+) Severe (4+)

CORONARY STATUS

45. Coronary angiography performed:

--	--

 month

--	--

 day

--	--	--	--

 year

46. Dominant coronary system: Right Left Co-dominant

47. Left main \geq 50% stenosis: No Yes

48. Diseased territories:

Single vessel disease Double vessel disease Triple vessel disease

49. Syntax Score:

--	--

 (www.syntaxscore.com)

--	--	--

--	--	--	--

--	--	--

CASS SITE CODES					
1 = Prox RCA	6 = 1 st RPL	11 = LMCA	16 = 2 nd Diag	21 = 2 nd OM	26 = 3 rd LPL
2 = Mid RCA	7 = 2 nd RPL	12 = Prox LAD	17 = 1 st Septal	22 = 3 rd OM	27 = LPDA
3 = Dist RCA	8 = 3 rd RPL	13 = Mid LAD	18 = Prox Cx	23 = Dist Cx	28 = RAMUS
4 = RPDA	9 = Inferior Septal	14 = Dist LAD	19 = Mid Cx	24 = 1 st LPL	29 = 3 rd Diag
5 = RPAV	10 = Acute Marginal	15 = 1 st Diag	20 = 1 st OM	25 = 2 nd LPL	30 = Unknown

CORONARY MAP:

	a.	b.	c.	d.	e.	f.																		
50. CASS Site	

 	 	

			

 	 	

			

 	 	

			

 	 	

			

 	 	

			

 	 	

								
51. Stenosis %	

 	 	 	

				

 	 	 	

				

 	 	 	

				

 	 	 	

				

 	 	 	

				

 	 	 	

			
52. Vessel Diameter (mm)	

 	.	 	

		.		

 	.	 	

		.		

 	.	 	

		.		

 	.	 	

		.		

 	.	 	

		.		

 	.	 	

		.	
	.																							
	.																							
	.																							
	.																							
	.																							
	.																							
53. PCI	 No  Yes	 No  Yes	 No  Yes	 No  Yes	 No  Yes	 No  Yes																		
54. Intent to bypass	 No  Yes	 No  Yes	 No  Yes	 No  Yes	 No  Yes	 No  Yes																		

a. If yes, Type of conduit to be used

a.	b.	c.	d.	e.	f.
 LIMA  RIMA  Radial Artery  Venous  Other <hr/>	 LIMA  RIMA  Radial Artery  Venous  Other <hr/>	 LIMA  RIMA  Radial Artery  Venous  Other <hr/>	 LIMA  RIMA  Radial Artery  Venous  Other <hr/>	 LIMA  RIMA  Radial Artery  Venous  Other <hr/>	 LIMA  RIMA  Radial Artery  Venous  Other <hr/>

SITE NO.	SUBJECT ID.	ALPHA CODE
		

PHYSICAL ASSESSMENT55. Height: cm56. Weight: . kg57. Body Surface Area (Mosteller Formula): . m²58. Body Mass Index (NHLBI Calculator): . kg/m²59. Ankle-Brachial Index (lower ABI) – **RIGHT**: (research procedure) . 60. Ankle-Brachial Index (lower ABI) – **LEFT**: (research procedure) . **CLINICAL LABORATORY DATA** (If no results available, leave blank)

61. HbA1c	 .  %	Date:    month day year
-----------	---	---

62. Potassium	 .  mEq/L	Date:     month day year
---------------	---	---

Serum plasma

63. Serum Creatinine	 .  mg/dL	Date:     month day year
----------------------	---	---

64. Plasma Creatinine	 .  mg/dL	Date:     month day year
-----------------------	---	---

65. eGFR (IDMS) < 60?	 No  Yes	Date:     month day year
-----------------------	--	---

66. C-Reactive Protein (hs-CRP)	 .  mg/dL	Date:     month day year
---------------------------------	---	---

67. White Blood Cell Count (WBC)	 .   ^{10³/mm³}	Date:     month day year
----------------------------------	--	---

68. Hematocrit (HCT)	 .  %	Date:     month day year
----------------------	---	---

SITE NO.	SUBJECT ID.	ALPHA CODE									
